#### 8.1.1. Adverse Events of Special Interest Analyses

Adverse events of special interest (AESIs) for closer monitoring are listed in Section [11.6.4](#).

Separate summary tables showing the number and percent of subjects with each type of AESI, broken down by preferred term will be created. Information will be reported as part of the standard AE tables for AESIs of infections, serious infections, neoplasms, cardiac disorders and serious cardiac disorders.

For each type of AESI a profile summary table will be produced containing information which would include, but not be limited to, the number of occurrences of the event, event characteristics, time to onset, intensity, outcome and action taken.

A listing of any subjects with systemic events identified by the investigators as meeting the criteria for anaphylaxis as outlined by the 2006 Joint National Institute of Allergy and Infectious Disease/Food Allergy and Anaphylaxis Network Second Symposium on Anaphylaxis [[Sampson, 2006](#)] will be provided

### 8.1.2. Cardiovascular Events and Deaths (All Causes)

Cardiovascular events and deaths (all causes) will be captured on targeted event pages of the CRF for the following AEs and SAEs:

- Myocardial infarction/unstable angina
- Congestive heart failure
- Arrhythmias
- Valvulopathy
- Pulmonary hypertension
- Cerebrovascular events/stroke and transient ischemic attack
- Peripheral arterial thromboembolism
- Deep venous thrombosis/pulmonary embolism
- Revascularization
- Death (all causes)

### 8.2. Clinical Laboratory Analyses

Laboratory evaluations including the analyses of Chemistry laboratory tests, Haematology laboratory tests, and liver function tests will be based on GSK Core Data Standards. The details of the planned displays are in [Appendix 11: List of Data Displays](#).

### 8.3. Other Safety Analyses

The analyses of non-laboratory safety test results including ECGs, vital signs and immunogenicity will be based on GSK Core Data Standards, unless otherwise specified. The details of the planned displays are presented in [Appendix 11: List of Data Displays](#).

#### 8.3.1. Immunogenicity

Immunogenicity is a measure of the immune response to a therapeutic drug (e.g. a monoclonal antibody) resulting in generation of anti-drug antibodies (see Section [11.6.4](#)).

A table will be produced summarising the number and percentage of subjects with negative and confirmed positive on-treatment ADA samples by treatment group and visit. The table will also summarise the highest assay result obtained whilst on-treatment for each subject. A similar table will also be produced summarising results for the neutralising antibody assay by treatment group and visit.

An additional summary of treatment emergent positive confirmatory binding antibody assay and results in the subset of subjects who did not have a positive confirmatory binding antibody assay result at the first dose of study treatment in each period (Parts A/B, Part C and Part D) will also be presented.

All immunogenicity results (i.e. ADA screening and confirmatory assay results, titre values, neutralising antibody results) will be listed.

The details of the planned Immunogenicity displays are presented in [Appendix 11: List of Data Displays](#).

## **9. BIOMARKER ANALYSES**

Blood (serum) samples were collected during Part C of the study and may be used for the purposes of measuring biomarkers to identify factors that may influence the development of asthma and/or medically related conditions, as well as the biological and clinical responses to mepolizumab.

A separate plan will be produced detailing any additional analysis of collected biomarker data.

## 11. APPENDICES

### 11.1. Appendix 1: Protocol Deviation Management and Definitions for Per Protocol Population

#### 11.1.1. Exclusions from Per Protocol Population

As detailed in Section 4.1 protocol deviations will be tracked by the study team throughout the conduct of the study in accordance with the Protocol Deviation Management Plan (PDMP) and important protocol deviations (including deviations related to study inclusion/exclusion/randomization criteria, conduct of the trial, patient management or patient assessment) will be listed and summarised.

Subjects with protocol deviations considered to potentially have an effect on efficacy will be removed from the Per Protocol (PP) population. Determination of the Per Protocol population will be performed whilst blinded to treatment, before the database is frozen. The reason for the exclusion of any subject will be documented.

A further review of the Per Protocol population will be performed following unblinding regarding protocol deviation criteria impacted by blinded study treatment (e.g. exclusion criteria number 5 below). Similarly the reason for the exclusion of any subject will be documented.

A subject meeting any of the following criteria will be excluded from the Per Protocol population:

Number	Exclusion Description
01	Randomization Inclusion Criterion #1 – Any subject without documented evidence of at least 3 years (156 weeks) of treatment with mepolizumab, with no treatment gaps of greater than 12 weeks (84 days) between any two doses at the time of randomization. See Section 11.6.2 for further details regarding the definition of continuous mepolizumab treatment.
02	Randomization Inclusion Criterion #3 – Any subject with changes in the dose or regimen of ICS, and/or additional controller medication during the fixed run-in period (Part B). N.B. This excludes the use of OCS for the treatment of an asthma exacerbation.
03	Any subject with changes in the dose or regimen of ICS, and/or additional controller medication during double-blind treatment (Part C). N.B. This excludes the use of OCS for the treatment of an asthma exacerbation.
04	Breaking of the treatment blind at any point during Part C of the study.
05	Receiving the incorrect study treatment at any point during Part C of the study (not the treatment to which the subject was randomized) [1].
06	Use of any prohibited medication during Parts B or C of the study [2].
07	Randomization Exclusion Criterion #6 – Current smokers at Visit C1.
08	Randomization Exclusion Criterion #7 – Subjects with an asthma exacerbation that has not resolved completely within 7 days of Visit C1.

- [1] This incorrect study treatment criteria will be re-assessed following unblinding, where an additional review of subject data will be performed. The reason for the exclusion of any subject will be documented.
- [2] See Protocol Section 7.9.2 for the list of prohibited medications within this study.

11.2. Appendix 2: Schedule of Activities

11.2.1. Protocol Defined Schedule of Events

Table 1 Time and Events Table: Screening/Variable Open-Label Run-In Weeks 0 - 52 - Part A

PART A Procedures	Pre-Screen 	Exit/EW Visit MEA115666 or 201312/ Screen 	Variable Open-Label Treatment Part A  (window is ± 1 week)													EW Visit 
			A1	A2	A3	A4	A5	A6	A7	A8	A9	A10	A11	A12	A13	
Visit	0	1														
Week of Variable Run-In		0	4	8	12	16	20	24	28	32	36	40	44	48	52	
Written Informed Consent	X															
Demography		X														
Medical History		X														
Assess cardiac risk factors		X														
Smoking status		X														
Inclusion/Exclusion Criteria		X														
Safety Assessments																
Concomitant Medication	X	X	X	X	X	X	X	X	X	X	X	X	X	X	X	X
Physical Examination		X												X		X
Vital Signs		X	X	X	X	X	X	X	X	X	X	X	X	X	X	X
12-lead ECG		X						X						X		X
Adverse Events	X	X	X	X	X	X	X	X	X	X	X	X	X	X	X	X
Laboratory Assessments																
Haematology		X						X						X		X
Chemistry (incl. LFT)		X						X						X		X
Pregnancy Test 		U	U	U	U	U	U	U	U	U	U	U	U	U	U	U
Immunogenicity		X												X		X
HbsAg and hepatitis C antibody		X														
Efficacy Assessments																
Exacerbation review	X	X	X	X	X	X	X	X	X	X	X	X	X	X	X	X

PART A Procedures	Pre-Screen 	Exit/EW Visit MEA115666 or 201312/ Screen 	Variable Open-Label Treatment Part A  (window is ± 1 week)													EW Visit 
			Visit	0	1	A1	A2	A3	A4	A5	A6	A7	A8	A9	A10	
Week of Variable Run-In		0	4	8	12	16	20	24	28	32	36	40	44	48	52	
Asthma Control Questionnaire-5		X			X			X			X			X		X
Spirometry		X						X						X		X
Worksheets/Diary/IP/ eCRF																
Administer open-label mepolizumab		X	X	X	X	X	X	X	X	X	X	X	X	X	X	
Dispense albuterol/salbutamol		X	X	X	X	X	X	X	X	X	X	X	X	X	X	
Collect albuterol/salbutamol			X	X	X	X	X	X	X	X	X	X	X	X	X	X
Dispense paper diary		X	X	X	X	X	X	X	X	X	X	X	X	X	X	
Collect/review paper diary			X	X	X	X	X	X	X	X	X	X	X	X	X	X
Contact IRT	X															X
Complete eCRF	X	X	X	X	X	X	X	X	X	X	X	X	X	X	X	X

1. The Pre-Screen Visit and Screening Visit may occur on the same day.
2. Visits should be conducted every 4 weeks until the subject has reached 3 years of mepolizumab exposure.
3. Please see the SRM for details on which screening procedures to perform for subjects entering from 201312 and MEA115666. ALL procedures should be completed prior to dosing with open-label mepolizumab.
4. Urine pregnancy tests (U) should be conducted for women of child bearing potential.
5. EW = Early Withdrawal. Should be conducted 4 ± 1 weeks from the subject's last dose

**Table 2 Time and Events Table: Screening/Variable Open-Label Run-In Weeks 56 - 132- Part A**

PART A Procedures	Variable Open-Label Treatment Part A  (window is ± 1 week)														EW Visit 
	Visit	A14/A27	A15/A28	A16/A29	A17/A30	A18/A31	A19/A32	A20/A33	A21	A22	A23	A24	A25	A26	
Week of Variable Run-In	56/108	60/112	64/116	68/120	72/124	76/128	80/132	84	88	92	96	100	104		
Safety Assessments															
Concomitant Medication	X	X	X	X	X	X	X	X	X	X	X	X	X	X	X
Physical Examination													X		X
Vital Signs	X	X	X	X	X	X	X	X	X	X	X	X	X	X	X
12-lead ECG					X								X		X
Adverse Events	X	X	X	X	X	X	X	X	X	X	X	X	X	X	X
Laboratory Assessments															
Haematology					X								X		X
Chemistry (incl. LFT)					X								X		X
Pregnancy Test 	U	U	U	U	U	U	U	U	U	U	U	U	U	U	X
Immunogenicity													X		X
Efficacy Assessments															
Exacerbation review	X	X	X	X	X	X	X	X	X	X	X	X	X	X	X
Asthma Control Questionnaire-5		X			X				X				X		X
Spirometry					X								X		X
Worksheets/Diary/IP/eCRF															
Administer open-label mepolizumab	X	X	X	X	X	X	X	X	X	X	X	X	X	X	
Dispense albuterol/salbutamol	X	X	X	X	X	X	X	X	X	X	X	X	X	X	
Collect albuterol/salbutamol	X	X	X	X	X	X	X	X	X	X	X	X	X	X	X
Dispense paper diary	X	X	X	X	X	X	X	X	X	X	X	X	X	X	
Collect/review paper diary	X	X	X	X	X	X	X	X	X	X	X	X	X	X	X
Contact IRT															X
Complete eCRF	X	X	X	X	X	X	X	X	X	X	X	X	X	X	X

1. Visits should be conducted every 4 weeks until the subject has reached 3 years of mepolizumab exposure.
2. Urine pregnancy tests (U) should be conducted for women of child bearing potential.
3. EW = Early Withdrawal. Should be conducted 4 ± 1 weeks from the subject's last dose

**Table 3 Time and Events Table: Fixed Run-In & Double-Blind Treatment Period – Parts B and C**

PARTS B&C Procedures	Fixed Run-in Part B		EW from Part B 	Randomization	Double-Blind Treatment Part C (window is ± 1 week)													IPDISC/EW Visit 
	Visit	B1			B2 	Part B EW	C1	C2	C3	C4	C5	C6	C7	C8	C9	C10	C11	
Week of Study	-4 ± 1	-4 ± 1 		0	4	8	12	16	20	24	28	32	36	40	44	48	52	
Smoking status				X														
Randomization Criteria				X														
Safety Assessments																		
Concomitant Medication	X	X	X	X	X	X	X	X	X	X	X	X	X	X	X	X	X	X
Physical Examination	X		X	X													X	X
Vital Signs	X	X	X	X	X	X	X	X	X	X	X	X	X	X	X	X	X	X
12-lead ECG	X		X							X							X	X
Adverse Events	X	X	X	X	X	X	X	X	X	X	X	X	X	X	X	X	X	X
Laboratory Assessments																		
Haematology	X		X	X	X	X	X	X	X	X	X	X	X	X	X	X	X	X
Chemistry (incl. LFT)	X		X	X						X							X	X
Biomarkers				X	X	X	X	X	X	X							X	X
Pregnancy Test 	U	U	U	U	U	U	U	U	U	U	U	U	U	U	U	U	U	U
Immunogenicity			X														X	X
Efficacy Assessments																		
Subject/Clinician Global Impression Rating				X			X			X			X				X	X
Subject/Clinician Rating of Response to Therapy							X			X			X				X	X
SGRQ				X			X			X			X				X	X

PARTS B&C Procedures	Fixed Run-in Part B		EW from Part B 	Randomization	Double-Blind Treatment Part C (window is ± 1 week)													IPDISC/EW Visit 	
	Visit	B1			B2 	Part B EW	C1	C2	C3	C4	C5	C6	C7	C8	C9	C10	C11		C12
Week of Study	-4 ± 1	-4 ± 1 		0	4	8	12	16	20	24	28	32	36	40	44	48	52		
Exacerbation review	X	X	X	X	X	X	X	X	X	X	X	X	X	X	X	X	X	X	X
Spirometry (pre- and post-albuterol/salbutamol)			X 	X			X			X			X					X	X
Healthcare resource utilization					X	X	X	X	X	X	X	X	X	X	X	X	X	X	X
Review eDiary  (symptoms, rescue use, nocturnal awakenings, PEF, ACQ-5, missed days of work/school)	←																		→
Worksheets/Diary/IP/ eCRF																			
Administer open-label mepolizumab 	X	X																	
Administer double blind study treatment				X 	X	X	X	X	X	X	X	X	X	X	X	X	X		
Dispense albuterol/salbutamol	X	X		X	X	X	X	X	X	X	X	X	X	X	X	X	X		
Collect albuterol/salbutamol	X	X	X	X	X	X	X	X	X	X	X	X	X	X	X	X	X	X	X
Dispense paper diary	X	X		X	X	X	X	X	X	X	X	X	X	X	X	X	X		
Dispense eDiary	X																		
Collect eDiary			X															X	X 
Collect/review paper diary	X	X	X	X	X	X	X	X	X	X	X	X	X	X	X	X	X	X	X
Contact IRT			X	X														X	X

PARTS B&C Procedures	Fixed Run-in Part B		EW from Part B 	Randomization	Double-Blind Treatment Part C (window is ± 1 week)													IPDISC/EW Visit 	
	Visit	B1			B2 	Part B EW	C1	C2	C3	C4	C5	C6	C7	C8	C9	C10	C11		C12
Week of Study	-4 ± 1	-4 ± 1 		0	4	8	12	16	20	24	28	32	36	40	44	48	52		
Complete eCRF	X	X	X	X	X	X	X	X	X	X	X	X	X	X	X	X	X	X	X

1. Visit B2 is only intended for subjects who experience an exacerbation in the run-in Part B which is not resolved within 7 days of Visit C1 or subjects who fail eDiary Compliance Criteria (Protocol Section 6.3).
2. All assessments to be completed prior to dosing.
3. Urine pregnancy tests (U) should be conducted every 4 weeks for women of child bearing potential.
4. Subjects eDiary entries should be reviewed by the site weekly during Part C
5. An unblinding card will be dispensed after Randomization at Visit C1.
6. The eDiary is only collected at an Early Withdrawal visit and not at IPDISC in Part C.
7. IPDISC/EW visit should be conducted 4 ± 1 weeks from the subject's last dose
8. Only *pre*-bronchodilator spirometry required at this visit.

**Table 4 Time and Events Table: Optional Open-Label Switch to Mepolizumab – Part D**

PART D Procedures	OPTIONAL Open-Label Switch to mepolizumab Part D  (window is ± 1 week)														IPDISC/EW Visit 
	Visit	D1	D2	D3	D4	D5	D6	D7	D8	D9	D10	D11	D12	D13	
Week of Study	0	4	8	12	16	20	24	28	32	36	40	44	48	52	
Safety Assessments															
Concomitant Medication	X	X	X	X	X	X	X	X	X	X	X	X	X	X	X
Physical Examination														X	X
Vital Signs	X	X	X	X	X	X	X	X	X	X	X	X	X	X	X
12-lead ECG							X							X	X
Adverse Events	X	X	X	X	X	X	X	X	X	X	X	X	X	X	X
Laboratory Assessments															
Haematology 				X			X			X				X	X
Chemistry (incl. LFT)							X							X	X
Pregnancy Test 	U	U	U	U	U	U	U	U	U	U	U	U	U	U	U
Immunogenicity														X	X
Efficacy Assessments															
Exacerbation review	X	X	X	X	X	X	X	X	X	X	X	X	X	X	X
Spirometry				X			X			X				X	X
Worksheets/Diary/IP/ eCRF															
Administer open-label mepolizumab	X	X	X	X	X	X	X	X	X	X	X	X	X		
Dispense albuterol/salbutamol	X	X	X	X	X	X	X	X	X	X	X	X	X		
Collect albuterol/salbutamol	X	X	X	X	X	X	X	X	X	X	X	X	X	X	X
Dispense paper diary	X	X	X	X	X	X	X	X	X	X	X	X	X		
Review eDiary  (symptoms, rescue use, nocturnal awakenings, PEF, ACQ-5, missed days of work/school)	X	X	X	X	X	X	X	X	X	X	X	X	X	X	X
Collect eDiary														X	X 

PART D Procedures	OPTIONAL Open-Label Switch to mepolizumab Part D  (window is ± 1 week)														IPDISC/EW Visit 	
	Visit	D1	D2	D3	D4	D5	D6	D7	D8	D9	D10	D11	D12	D13		Exit Visit
Week of Study 	0	4	8	12	16	20	24	28	32	36	40	44	48	52		
Collect/review paper diary	X	X	X	X	X	X	X	X	X	X	X	X	X	X	X	X
Contact IRT															X	X
Complete eCRF	X	X	X	X	X	X	X	X	X	X	X	X	X	X	X	X

1. The combined treatment period (Part C) and any switch to open-label mepolizumab (Part D) should not exceed a total duration of 52 weeks.
2. Subjects may enter the Open-label Switch Part D at any point during Part C provided they meet switch criteria, starting with the week of study that the switch is made and continuing until week 52, discontinuation of IP or early withdrawal.
3. All assessments to be completed prior to dosing
4. Haematology samples will be collected for each of the subject's first 3 visits of Part D, and then according to designated Visits in [Table 4](#)
5. Urine pregnancy tests (U) should be conducted every 4 weeks for women of child bearing potential.
6. The eDiary should be reviewed at each visit. Weekly review is not required in Part D.
7. The eDiary is only collected at an Early Withdrawal or Exit visit.
8. IPDISC/EW visit should be conducted 4 ± 1 weeks from the subject's last dose

## 11.3. Appendix 3: Assessment Windows and Visit Slotting

### 11.3.1. Analysis Visit Labels

When summarising data within Parts A/B of the study nominal clinic visit will be presented (in weeks) relative to the date of first dose of open-label treatment (Parts A/B). For example:

Screening = Week 0  
Visit A1 = Week 4  
Visit A2 = Week 8  
etc.

When summarising data within Part C of the study nominal clinic visit will be presented (in weeks) relative to the date of first dose of double-blind treatment (Part C). For example:

Visit C1 = Week 0  
Visit C2 = Week 4  
Visit C3 = Week 8  
etc.

When summarising data within Part D of the study nominal clinic visit will be presented (in weeks) relative to the clinic visit where each subject received the first dose of open-label treatment within Part D. For example, if a subject switched to open-label mepolizumab at Visit D4:

Visit D4 = Week 0  
Visit D5 = Week 4  
Visit D6 = Week 8  
etc.

See Section 11.6.1 for the presentation of study days with each reporting period.

### 11.3.2. Visit Based Assessments

In some circumstances certain Visit 1 (Screening) assessments will not be performed and assessments will be copied forward from each subject's last clinic visit from the precursor studies MEA115666/201312. Refer to Section 5.2.3 for more details.

All other visits are scheduled to take place as specified in [Appendix 2: Schedule of Activities](#). No assessment windows are defined for visit based assessments, hence measurements outside visit windows will not be excluded from analyses. For all clinic visits, nominal visit days and times will be used for reporting, such that if a subject recorded values that were outside of the  $\pm 7$  day window for a visit the subject will still be analysed under that visit.

See Section 11.3.3 and Section 11.3.4 for details regarding the slotting of data collected at an Early Withdrawal/Treatment Discontinuation Visit and unscheduled data to clinic visits for analysis.

### 11.3.3. Early Withdrawal / Treatment (IP) Discontinuation Visits

If a subject completes an Early Withdrawal or Treatment Discontinuation Visit at a visit where endpoint data were not scheduled to be collected, the data will be summarised and analysed (as appropriate) together with other data recorded as scheduled at the nominal visits according to the Time and Events schedule ([Appendix 2: Schedule of Activities](#)).

#### **Parts A/B**

Subjects who discontinue open-label mepolizumab/withdraw from study participation during Part A/B were expected to return to the clinic for an Early Withdrawal (EW) visit and to return any study materials approximately 4 weeks following their last dose of open-label mepolizumab. No additional follow-up is needed.

If a subject completes a Parts A/B Early Withdrawal Visit at a scheduled visit at which endpoint data were not scheduled to be collected, data will be slotted to the nearest adjacent visit within Part A/B where the endpoint data was scheduled to be collected according to the Time and Events schedule ([Appendix 2: Schedule of Activities](#)) unless data are already recorded at that visit.

#### **Part C or Part D**

Subjects who withdrew prematurely from treatment or from the study during Part C or Part D may have data recorded under either a nominal visit at which it was scheduled for collection, a nominal visit at which it was not scheduled for collection, or an early withdrawal/IP discontinuation visit.

Subjects switching from treatment within Part C to Part D following an asthma exacerbation are required to complete an IP discontinuation/switch visit with a full set of assessments at each subject's first Part D visit, prior to first dose with open-label mepolizumab per [Appendix 2: Schedule of Activities](#). Such IP discontinuation/switch visits will be handled as a Treatment Discontinuation Visit as discussed below and data will attempt to be slotted to the nearest adjacent visit within Part C where the endpoint data was scheduled to be collected according to the Time and Events schedule ([Appendix 2: Schedule of Activities](#)) unless data are already recorded at that visit

If a subject was withdrawn from the study for any reason the Investigator must make every effort to have the subject to return to the clinic for an EW Visit approximately 4 weeks following the last dose to perform EW Visit assessments and to return all study-related materials. Assessments are described in [Appendix 2: Schedule of Activities](#).

Subjects in study Part C or Part D who have permanently discontinued double-blind or open-label IP were not required to withdraw from the study. Subjects who have permanently discontinued IP and have not withdrawn consent may have continued in the study off-treatment.

Subjects wishing to remain in the study will have completed an IP Discontinuation Visit (approximately 4 weeks after the last dose at the same time as the next scheduled visit) and continued to attend the clinic visits at the protocol designated time intervals and completed eDiary daily and weekly entries for important efficacy and safety assessments.

If the subject was unable to visit the clinic to complete any study assessments which require physical presence of the subject, visits could have continued to occur by telephone contact to review exacerbations, adverse events and concomitant medications.

Subjects who have previously discontinued IP and have already completed their IP Discontinuation Visit (approximately 4 weeks following the last dose) but then decided at a later date that they no longer wish to participate in the study, will be asked to return to the clinic to complete an EW Visit approximately 4 weeks following the last clinic visit to complete any EW assessments and to return any remaining study materials. No additional safety follow-up visit is required.

If a subject completes an Early Withdrawal or Treatment Discontinuation Visit in Part C or Part D at a scheduled visit at which endpoint data were not scheduled to be collected, data will be slotted to the nearest adjacent visit within the appropriate reporting period (Part C or Part D) where the endpoint data was scheduled to be collected according to the Time and Events schedule ([Appendix 2: Schedule of Activities](#)) unless data are already recorded at that visit.

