
 
A composite estimand strategy will be applied in the handling of the intercurrent event of discontinuation of double-blind treatment.
 
Subjects will be categorized during the On-treatment (Part C) period according to their questionnaire (ACQ-5 / SGRQ) response. Following treatment discontinuation (end of On-treatment [Part C] phase) subjects will be shown as missing and on analysis included in the least favorable category of increase from baseline of <math>\geq 0.5</math> units or <math>\geq 4</math> units for the ACQ-5 and SGRQ endpoints, respectively.
 
Subjects will be analysed according to the treatment received for more than 50% of injections within Part C (see Section 5.1).
 
All subjects will be considered on-treatment from their first dose of double-blind treatment at visit C1. Subjects who complete Part C will be considered on-treatment up to their Week 52 (Exit Visit/C14) visit date. Subjects who discontinued double-blind treatment will be considered on-treatment until the time of treatment discontinuation. 
 
Questionnaires: see On-treatment (Part C) definition within Section 11.4.3
 
 
 

Model Specification

 
Logistic regression will be used to compare the proportion of patients achieving a 0.5 units / 4 point or greater increase from baseline in ACQ-5 / SGRQ Total Score between treatment groups at each analysis visit (separate models will be used for each analysis visit).
 
Subjects with a missing response at a particular visit will be included in the least favorable category as having a 0.5 units / 4 point or greater increase from baseline in ACQ-5 / SGRQ Total Score in the logistic regression model for the analysis of that visit.
 
Terms fitted in each logistic regression model will include: 
 
Fixed Categorical Covariates: Treatment, Region, Baseline maintenance OCS use [Visit C1]
 
Fixed Continuous Covariates: Baseline Score, Exacerbations in the year prior to randomization [Visit C1] (as an ordinal variable)
 
 
 
 
See Section 5.4.1 for further details around model covariates.

Model Checking & Diagnostics

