
 
A composite estimand strategy will be applied in the handling of the intercurrent event of discontinuation of double-blind treatment.
 
Subjects will be categorized during the On-treatment (Part C) period according to their response. Following treatment discontinuation (end of On-treatment [Part C] phase) subjects will be shown as missing and on analysis included in the least favorable category of the respective outcome.
 
Subjects will be analysed according to the treatment received for more than 50% of injections within Part C (see Section 5.1).
 
All subjects will be considered on-treatment from their first dose of double-blind treatment at visit C1. Subjects who complete Part C will be considered on-treatment up to their Week 52 (Exit Visit/C14) visit date. Subjects who discontinued double-blind treatment will be considered on-treatment until the time of treatment discontinuation. 
 
Questionnaires: see On-treatment (Part C) definition within Section 11.4.3
 
 
 

Model Specification

 
Ordinal logistic regression (proportional odds model) will be used to compare the proportion of patients in each response category between treatment groups at each analysis visit (separate models will be used for each analysis visit).
 
Subjects with a missing response at a particular visit will be included in the least favorable category of the respective outcome in the ordinal logistic regression model for the analysis of that visit.
 
Terms fitted in each ordinal logistic regression model will include: 
 
Fixed Categorical Covariates: Treatment, Baseline (Global impression of asthma severity rating only), Region, Baseline maintenance OCS use [Visit C1]
 
Fixed Continuous Covariates: Exacerbations in the year prior to randomization [Visit C1] (as an ordinal variable)
 
 
 
 
See Section 5.4.1 for further details around model covariates.

Model Checking & Diagnostics

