**11.4.3. Treatment Phases (Visit Based Efficacy and Safety Data)**

Visit based efficacy data, safety data and eDiary data will be classified into treatment phases according to the time of occurrence/assessment relative to the dates of the study treatment and/or the participation of subjects within specific study parts (as dictated by attendance at specific visits) as shown in the table below:

Treatment Phase	Definition
Pre-treatment	Date & time $\leq$ First dose of open-label mepolizumab
On-treatment (Parts A/B)	Subjects who are randomized and receive double-blind treatment: First dose of open-label mepolizumab < Date & time $\leq$ First dose of double-blind treatment Subjects who are not randomized: First dose of open-label mepolizumab < Date & time $\leq$ Earliest of (1) Last dose of open-label mepolizumab + 28 days or (2) Early Withdrawal visit date 
Post-treatment (Parts A/B)	Subjects who are not randomized: Date & time > Earliest of (1) Last dose of open-label mepolizumab + 28 days or (2) Early Withdrawal visit date 
On-treatment (Part C)	Subjects completing study Part C: First dose of double-blind treatment < Date & time $\leq$ C14 (Exit Visit) visit date Subjects discontinuing study treatment/withdrawing early from within Part C: First dose of double-blind treatment < Date & time $\leq$ Earliest of (1) Last dose of double-blind treatment + 28 days or (2) Early Withdrawal / IP Discontinuation visit date Subjects who switch to study Part D: First dose of double-blind treatment < Date & time $\leq$ First dose of open-label mepolizumab within Part D
Post-treatment (Part C)	Subjects completing study Part C: Date & time > C14 (Exit Visit) visit date Subjects discontinuing study treatment/withdrawing early from within Part C: Date & time > Earliest of (1) Last dose of double-blind treatment + 28 days or (2) Early Withdrawal / IP Discontinuation visit date
On-treatment (Part D)	Subjects completing study Part D: First dose of open-label mepolizumab within Part D < Date & time $\leq$ D14 (Exit Visit) visit date Subjects discontinuing study treatment/withdrawing early from within Part D: First dose of open-label mepolizumab within Part D < Date & time $\leq$ Earliest of (1) Last dose of open-label mepolizumab within Part D + 28 days or (2) Early Withdrawal / IP Discontinuation visit date

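### The visit-slotting rule in SAP 11.3.3 can fill a later analysis visit with a switch-day or discontinuation SGRQ or rating, where the composite rule in SAP 7.3.2.1 calls for the least favourable category

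*SAP*

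**What the plan says.** **Slotting (SAP 11.3.3, Part C or Part D).** A subject who moves to Part D has an "IP discontinuation/switch visit with a full set of assessments at each subject's first Part D visit, prior to first dose with open-label mepolizumab". For those data, "data will attempt to be slotted to the nearest adjacent visit within Part C where the endpoint data was scheduled to be collected", unless a value is already recorded at that visit. A parallel sentence covers other early withdrawal and IP discontinuation visits. Neither gives a direction in time, and neither treats the composite endpoints separately.

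**Composite strategy (SAP 7.3.2.1).** For the ACQ-5 and SGRQ responder endpoints: "Following treatment discontinuation (end of On-treatment [Part C] phase) subjects will be shown as missing and on analysis included in the least favorable category". For the global impression and response-to-therapy ratings: "subjects will be shown as missing and on analysis included in the least favorable category of the respective outcome". In the logistic model the failure is assigned through absence of data: a subject is put in the worsened category at a visit when no response is available for that visit. The ordinal model for the ratings works in the same way.

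**End of the phase (SAP 11.4.3).** For switchers, On-treatment (Part C) ends at the first open-label dose in Part D. For others who stop, it ends at the "Earliest of (1) Last dose of double-blind treatment + 28 days or (2) Early Withdrawal / IP Discontinuation visit date".

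**Schedule (SAP Appendix 2, Tables 3 and 4).** SGRQ and the global impression are collected at C1 and at Weeks 12, 24, 36 and 52. Response to therapy is collected at the same weeks but not at C1. Part D schedules none of the three.

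**The concern.** Following both rules as written gives two results for one subject. Someone who switches at Week 32 completes the SGRQ before the first open-label dose, so by date the value is on-treatment. The nearest scheduled SGRQ visit is Week 36 (4 weeks ahead, against 8 weeks back to Week 24), and nothing collected in Part D occupies it. The Week 32 value becomes the Week 36 response. The response is then not missing, so the failure rule in the model does not operate, although the subject left double-blind treatment four weeks before.

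A subject who switches at Week 28 has Week 24 as the nearest visit. It is normally filled, so Week 36 is missing and counts as a failure. The same intercurrent event is handled in opposite ways according to the week in which it happens. More switching is expected on placebo, so the lost failures would not be balanced between arms.

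**Working it through.** **1. The plan's own figures.** Inputs from Protocol 5.3 and 10.2.1: 150 per arm, 40% with an event on mepolizumab, 60.5% on placebo, 20% withdrawing before an event, about 120 switchers.

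- Switchers: 0.8 × 300 × (0.40 + 0.605)/2 = 120.6, against about 120 stated.
- Hazard ratio: ln(0.60)/ln(0.395) = 0.550, as stated.

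**2. Where each off-schedule visit goes (SGRQ, strict nearest-visit reading).**

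| Switch or discontinuation week | Nearest scheduled visit | Consequence |
|---|---|---|
| 4 | 0 | Already recorded, so Week 12 is a failure |
| 8 | 12 | Fills Week 12 |
| 16 | 12 | Normally recorded, so Week 24 is a failure |
| 20 | 24 | Fills Week 24 |
| 28 | 24 | Normally recorded, so Week 36 is a failure |
| 32 | 36 | Fills Week 36 |
| 40 | 36 | Normally recorded, so Week 52 is a failure |
| 44 | Tie, 36 and 52 | No rule given |
| 48 | 52 | Fills Week 52 |

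Response to therapy has no C1 assessment, so a Week 4 value goes to Week 12.

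**3. How many subjects.** Assume a constant hazard, and that every exacerbator who has not withdrawn switches at the next 4-weekly visit. Expected switchers per arm at Week w = 150 × 0.8 × [exp(−λ(w − 4)) − exp(−λw)], with λ = −ln(1 − p)/52. This gives λ = 0.00982 per week on mepolizumab and 0.01786 on placebo.

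| Switch week → analysis visit | Mepolizumab | Placebo |
|---|---|---|
| 8 → 12 | 4.4 | 7.7 |
| 20 → 24 | 4.0 | 6.2 |
| 32 → 36 | 3.5 | 5.0 |
| 48 → 52 | 3.0 | 3.8 |
| Total | 14.9 | 22.7 |

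If half switch, these halve. For response to therapy, Week 4 adds 4.6 and 8.3, so Week 12 alone has about 9.1 and 16.0. If an occupied nearest visit meant trying the other adjacent one, the SGRQ totals would be about 34 and 51.

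**4. Illustrative effect on the SGRQ odds ratio (mepolizumab/placebo, for failure).** Take every subject who switched before the visit as a failure, no other withdrawals, and 20% of the remainder as failures (assumed).

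- Week 12, composite rule prevails: failures are 9.1 + 0.2 × 140.9 = 37.3 and 16.0 + 0.2 × 134.0 = 42.8. Odds ratio (37.3/112.7)/(42.8/107.2) = 0.83. Standard error of the log odds ratio: √(1/37.3 + 1/112.7 + 1/42.8 + 1/107.2) = 0.26.
- Week 12, slotting prevails and half the slotted values are below the threshold: failures 35.1 and 38.95, odds ratio 0.87, a log shift of about 0.05.
- Week 12, all slotted values below the threshold: failures 32.9 and 35.1, odds ratio 0.92, a log shift of about 0.10. If none are below the threshold, nothing changes.
- Week 36, with 32.4 and 52.2 earlier switchers: failures 55.9 and 71.8, odds ratio 0.65. With half reclassified 0.66, with all 0.67.
- Replacing 20% by 0% or 40% at Week 12, with half reclassified, gives 0.54 to 0.54 and 0.89 to 0.93.

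**The case against.** The best defence is that the plan has a coherent convention. SAP 7.3.2.1 categorises subjects on their responses during the on-treatment period. SAP 11.4.3 makes the pre-dose switch-day value on-treatment by date. SAP 11.3.2 applies no visit windows, and SAP 11.3.3 says discontinuation data are analysed with data from nominal visits. The last on-treatment value would then be used once, under a nominal label, and the subject would fail afterwards. The sponsor may have meant this. But the SAP does not say so, and its composite text says that after the phase ends the subject is shown as missing. The target visit lies after that end.

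Other points stand and limit the concern:

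- A reader might infer that all discontinuation data are carried forward to the next scheduled visit. The text says nearest adjacent, and only if that visit is empty. A subject who stops treatment but stays in the study and supplies data at the target visit is not affected, because that value blocks the slot.
- A reader might assume a fixed share, such as half, is moved from failure to success. No document gives one. For SGRQ it could be low: recall is 4 weeks and switchers have recently exacerbated, so many values may already be 4 or more units worse. This argument is weaker for the ratings, where the worst category is more extreme.
- Any pull is towards 1 if the share is similar across arms, which is conservative for the superiority hypothesis.

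**Conclusion.** The two rules conflict and no passage says which prevails. On the strict nearest-visit reading, SGRQ and rating values from Weeks 8, 20, 32 and 48, and from Week 4 for response to therapy, replace a failure that the composite strategy requires. Those affected are mainly Part D switchers and early withdrawals. The SGRQ count of about 23 placebo and 15 mepolizumab rests on the planned event rates, a constant hazard and universal switching at the next visit. The share whose category changes is unknown (0% to 100%). In the illustration, reclassifying half moves the Week 12 log odds ratio by about one fifth of its standard error, and the Week 36 odds ratio by about 0.01.

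A reader might take this as a threat to the trial's conclusions. The documents do not support that. These are exploratory endpoints without multiplicity control (SAP 5.5, 7.3). The primary and secondary analyses do not use the composite strategy. The ACQ-5 responder analysis is protected by the dated weekly windows in SAP 11.3.5: the Week 32 switcher is a failure at Week 36 for ACQ-5 but is scored on a value for SGRQ, although one composite paragraph covers both.

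**What to change.** Add to SAP 11.3.3, with a cross-reference in 7.3.2.1, before unblinding: for endpoints under the composite strategy (SGRQ responder, global impression, response to therapy), data from an IP discontinuation, early withdrawal or switch visit at which the endpoint is not scheduled are not slotted to a later nominal visit falling after the end of On-treatment (Part C). The subject is in the least favourable category at that visit and all later ones. Leave slotting unchanged for the MMRM endpoints.

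The cost is a sentence and a flag in the responder and rating datasets. The measured value drops out of these models but stays in the SGRQ MMRM or, for the ratings, in the listings. The downside is that the SGRQ responder and SGRQ MMRM tables will use different data for these subjects at that visit, which a footnote can explain.
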